D.2.1 Overview of study approach: We will conduct a hybrid type 1 effectiveness-implementation study, using a pragmatic, open label RCT. We will recruit 270 hospitalized patients with (a) CP and (b) opioid misuse or OUD, randomize them 1:1 to BUP microdosing or TAU, and link them to outpatient BUP treatment. We will assess BUP treatment uptake (primary outcome) and other OUD and pain outcomes. The microdosing arm will use a 5-day BUP microdosing protocol (see **Figure E-2** and **Table E-2**) – BUP doses will be gradually increased while a full opioid agonist is continued. In the TAU arm, participants will stop other opioids and wait until they are in moderate opioid withdrawal before starting BUP. Both arms will receive follow-up care at Montefiore clinics to continue BUP treatment (with buprenorphine-naloxone) and manage CP. Assessment visits will occur at baseline, 1 week, and 1, 3, and 6-months. We will use EMA to assess opioid- and pain-related symptoms during induction and three 1-week periods over 3 months. We will also collect detailed information on microdosing implementation and cost-effectiveness.

D.2.2 Setting. We briefly describe study sites below and details are provided in the Facilities section. Montefiore Medical Center is the largest healthcare provider in The Bronx. The neighborhoods served by Montefiore are representative of low-income urban areas: over 65% of patients have public insurance, 57% Hispanic and 39% Non-Hispanic Black, and neighborhoods have been devastated by drug use. There are three Montefiore hospitals in the Bronx. Hospitalized medical patients are typically cared for by hospitalists with the availability of pain, addiction medicine, and psychiatry consultants. Montefiore also has 20 community health centers, the BUP Treatment Network (situated in 7 community clinics), and 5 opioid treatment programs. In outpatient settings, patients receive BUP treatment integrated with primary care services.

D.2.3 Participant Eligibility: We will enroll hospitalized patients with CP and opioid misuse or OUD who are taking opioids and eligible for BUP treatment. Opioid misuse will be defined as heroin use or prescription opioid misuse (defined as: 1) use without a prescription; 2) use in greater amounts, or more often than prescribed 3) running out of prescription pain medication early).¹⁰⁷ CP will be defined as pain that is chronic

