3	Full dose	2 mg q8	6 mg	--	8 mg BID	16 mg
4	Full dose	4 mg q8	12 mg	--	8 mg BID	16 mg

D.2.7 Clinical Protocols: Microdosing**(Experimental arm):**

Participants randomized to microdosing will start low-dose BUP while continuing a full opioid agonist according to a 4-day protocol (see **Figure E-2 & Table E-2**). Participants will be assessed for opioid withdrawal using the clinical opioid withdrawal scale (COWS) before the first BUP dose and 30 minutes after each administered dose while hospitalized.¹¹¹ A full opioid agonist will be continued until day 5 of the protocol.^{112,113} If patients are planned for discharge before completing

microdosing, they will receive at the time of discharge pre-packed medication clearly marked with the timing for each dose, instructions on how to take the medication and when to stop full agonist opioids. Opioid withdrawal will be assessed with the Subjective Opioid Withdrawal Scale (SOWS) via telephone.

Rationale for 5-day protocol: Published microdosing protocols range from 3 to 7 days or more. From 2012-2016, the mean length of stay for patients at Montefiore Medical Center with an opioid positive urine drug test was 7.62 days (95% CI: 7.44-7.80). Some evidence suggests that rapid titration to maintenance BUP treatment dosages prevents drop-out,¹¹⁴ but rapid titration could increase precipitated withdrawal risk, therefore, we developed our protocol in the middle of the published range.

TAU (Control arm): Participants randomized to TAU will receive a standard BUP induction following clinical guidelines. Full opioid agonists will be stopped and a clinician will assess for withdrawal using the COWS scale. If participants have a COWS score of ≥ 8 they will be eligible to receive a 2 mg BUP dose. Participants will be reassessed for withdrawal 30 minutes after receiving their first BUP dose.

Withdrawal management: Participants with COWS score increases of $\geq 50\%$ or an absolute increase of 4 or more will be considered to have precipitated withdrawal. If this occurs, induction will be postponed to the following day. Clinicians can administer non-opioid adjunctive medications (i.e., clonidine, loperamide) during induction based on hospital protocols. Medication use will be considered a covariate in analyses with withdrawal symptoms as an outcome.

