H₁: *The microdosing arm (vs. TAU) will have better BUP treatment uptake and retention, and less illicit opioid use.* Our primary analysis will be a logistic regression comparing the proportion of participants in each study arm who meet our definition of BUP uptake (see D.2.10). Secondary analyses will examine BUP retention and illicit opioid use as secondary outcomes. We will use a mixed effects logistic regression model to examine BUP retention at 1, 3, and 6 months and a mixed effects linear regression model to examine number of days of illicit opioid use (over 30 days) at 1, 3, and 6 months. Study arm will be considered a fixed effect, and participant and time (months) will be considered random effects. Additional analyses will include key variables mentioned above as covariates and potential confounders if they differ by study arm.

H₂: *Improvements in H₁ will be mediated by opioid- and pain-related symptoms.* Based on the model

described in **Figure E-3**, we will use structural equation modeling to determine whether improvements in OUD outcomes are due to improvements in opioid- and pain-related symptoms. We will use EMA data (5 random reports per day) and data from in-person visits at baseline, 1 week, 1, 3, and 6 months. For example, when the dependent variable is BUP uptake, we will calculate the standardized total effect from the intervention (BUP microdosing) to BUP uptake, as well as the standardized mediational (i.e., indirect) effect of opioid- and pain-related symptoms (e.g., withdrawal). The mediational effect is calculated as the product of the effect from intervention to the mediator, and the effect from the mediator to the outcome. To account for the influence of the baseline measures (e.g., sociodemographic characteristics) on the outcome and the mediator, we will use a partial correlation matrix as the input matrix. This will be created by statistically parsing out the effects of the baseline measures cited above on the mediator and the outcome variable. Our proposed model will be estimated using Mplus.¹³⁰ Overall model fit will be assessed by: (1) the root mean

[figure not shown]

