effect of opioid- and pain-related symptoms (e.g., withdrawal). The mediational effect is calculated as the product of the effect from intervention to the mediator, and the effect from the mediator to the outcome. To account for the influence of the baseline measures (e.g., sociodemographic characteristics) on the outcome and the mediator, we will use a partial correlation matrix as the input matrix. This will be created by statistically parsing out the effects of the baseline measures cited above on the mediator and the outcome variable. Our proposed model will be estimated using Mplus.¹³⁰ Overall model fit will be assessed by: (1) the root mean

square error of approximation (RMSEA), (2) Bentler's comparative fit index (CFI),¹³¹ and (3) the standardized root mean square residual (SRMR). To account for non-normal distribution of the model variables (e.g., BUP uptake), we will use Mplus's maximum likelihood with robust standard errors (MLR) as the estimator.

Aim 2: To test the effectiveness of microdosing (vs. TAU) on pain outcomes.

H₃: The microdosing arm (vs. TAU) will have less pain intensity and interference, and improved quality of life. We will use separate mixed effects linear regression models to compare each pain outcome from baseline to 3 months. Main analyses will use data from in-person visits at baseline, 1 week, 1 and 3 months. Study arm will be considered a fixed effect, and participant and time will be considered random effects. In additional analyses, we will include key variables mentioned above as covariates and potential confounders if they differ by study arm. We will also examine sustainability of outcomes at 6 months.

H₄: Improvements in H₃ will be mediated by OUD outcomes. Based on the model described in **Figure E-4**

and similar to the analyses for H2 (see above), we will use structural equation modeling to determine whether improvements in pain outcomes are due to improvements in OUD outcomes. For example, when the dependent variable is pain intensity, we will calculate the standardized total effect from the intervention (BUP microdosing) to pain reduction at 3 months, as well as the standardized mediational (i.e., indirect) effect of BUP uptake, BUP retention, and illicit opioid use. For these analyses, our primary mediator is BUP retention. We will use both the EMA data (5 random reports per day) and data from in-person visits at baseline, 1 week, 1 and 3 months.

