D.3.4 Qualitative data collection: [name] (early-stage investigator) or an RA will conduct 45-60 minute semi-structured interviews with participants and hospital providers. We will sample 20-30 participants in the microdosing arm, including those who do and do not initiate BUP. Participant interviews will occur after BUP induction. We will also interview 10 hospital providers who care for study participants. After completing interviews, if new themes continue to emerge, we will randomly select additional participants until thematic saturation is achieved. Patient interviews: We will develop a semi-structured interview guide with input from people with lived experience that asks open-ended questions about patients' experiences with induction, particularly acceptability and reasons for BUP initiation or lack of initiation, and whether BUP helps with pain. Provider interviews will elicit information about factors associated with achieving RE-AIM outcomes (reach, effectiveness, adoption, implementation, and maintenance). The interview guide will be informed by CFIR domains regarding implementation of induction and referral procedures at the hospitals. Using the 5 CFIR domains, we will probe how various factors enable or hinder implementing the microdosing protocol. This includes ease of initiating BUP (e.g., feasibility), inner organization (e.g., fit and acceptability within hospitals), outer setting (e.g., social factors influencing clinical practice), perceptions of individuals involved (e.g., BUP

Table E-6: Aim 3a Implementation Measures

Construct	Quantitative Measures	Qualitative Assessment
Reach	# and % of pts with CP and OUD screened # and % of pts with CP and OUD enrolled # and % of pts with CP and OUD ineligible Rates of enrollment at each hospital	Log of verbatim reasons patients stated for declining enrollment
Adoption	# and % of participants assessed for induction # and % of participant completing induction # and % of participants referred for outpatient BUP treatment # and % of participants linked to outpatient BUP treatment	Interviews with participants about their experience, including barriers and facilitators to treatment initiation and linkage
Implementation	# and % of participants who receive ≥ 1 dose of BUP within assigned induction protocol Intervention fidelity check-list	Interviews with providers about barriers and facilitators to implementation

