Maintenance	# of hospitals (of 3) conducting microdosing 3m after grant	Interviews with providers about current practices

perceived benefits), and implementation processes (e.g., protocol adaptation). Questions will identify barriers, such as provider stigma about OUD, and facilitators, such as leadership endorsement of protocols.

D.3.5 Analytic Plan: Interviews will be audio-recorded, digitally stored on an encrypted password protected computer, and professionally transcribed without participant identifiers. We will use thematic analysis to identify key themes relating to BUP initiation and implementation. *Initial review of data:* In an iterative process, [name] and team will read all interview transcripts and record concepts that emerge upon repeated readings.

Developing a coding scheme: The coding scheme will be based on the interview data and the goals of this project. The codebook will be discussed and agreed upon by the entire research team. Any necessary changes will be made by consensus. *Coding:* Using the codebook, two research team members will code data independently. The research team will meet, discuss codes, and, if there are any inconsistencies, will come to a consensus agreement as to application of codes for each transcript. Using Dedoose software (SocioCultural Research Consultants, Los Angeles CA), codes will be applied to the dataset and data will be organized by code. *Sorting:* After data are sorted and main themes are identified, the research team will meet again to ensure that all concepts are properly represented and that thematic saturation has occurred. *Member-checking:* Identified themes will be presented to study participants to elicit interpretation and additional insight.

D.4 Aim 3b: To calculate costs and examine cost-effectiveness of the BUP microdosing protocol

H₅: Compared with TAU, microdosing will be cost-effective from a societal and a health sector perspective. Following recommendations of the Second Panel on Cost-effectiveness in Health and Medicine,¹³⁴ we will take two reference case perspectives: a health care sector perspective and a societal perspective, over a 6-month time horizon. We will use quality-adjusted life years (QALYs), a key indicator for patient wellbeing, as the effectiveness measure.¹³⁴ Health Related Quality of Life (HRQoL) at discrete time points will be measured using a utility score resulting from the PROMIS-Preference (PROPr) system.¹²³

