For each reference case perspective, to estimate the incremental HRQoL and costs associated with the intervention – BUP microdosing vs. TAU – we will use intent-to-treat design and estimate a mixed Generalized Linear Model of the HRQoL/costs at the patient-level and at each assessment point as a function of patient assignment to microdosing (vs TAU), site fixed effects, and patient characteristics bearing implications for the outcomes but possibly not balanced at baseline, with random effects at patient and site levels.¹⁴⁶ The method of recycled predictions will be used to obtain predicted mean values for HRQoL and each cost category, by study arm. QALYs gained will be estimated using the area under the curve methodology.¹⁴⁷⁻¹⁴⁹ Predicted costs from different cost categories will be summed and tested according to relevant perspectives.¹⁴⁹ We will derive predicted *incremental* costs for intervention vs TAU for each individual patient based on the estimated models.

Cost-effectiveness analysis (CEA) will estimate an incremental cost-effectiveness ratio (ICER) associated with BUP microdosing vs. TAU. The ICER will be calculated by dividing (mean) incremental cost associated with microdosing vs TAU by (mean) incremental effectiveness. Sampling uncertainty in the estimated ICER will be taken into account by bootstrapping the study sample of the individual-level incremental cost and incremental effectiveness estimates and deriving non-parametric confidence intervals. We will further construct ICER acceptability curves for both reference case perspectives. Acceptability curves display the probability that an ICER would fall below a given willingness to pay for an incremental unit of the desired outcome and thus be considered a good value (that is, cost-effective).^{150,151}

D.5 Design considerations and limitations:

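### The Aim 3b cost model enters site as both a fixed and a random effect, so the site variance cannot be estimated; separately, hospital is missing from the H1 and H3 models, at some cost in precision only

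*Combined protocol and SAP*

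**What the plan says.** **Three hospitals take part.** Section D.2.2 introduces the study sites and states "There are three Montefiore hospitals in the Bronx". That sentence describes the setting; Table E-6 is firmer evidence of participation. Its reach measures include "Rates of enrollment at each hospital", and its maintenance measure is the number "of hospitals (of 3) conducting microdosing 3m after grant".

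**H1 and H3 models (D.2.11).** For uptake: "Our primary analysis will be a logistic regression comparing the proportion of participants in each study arm". The mixed models for retention, illicit opioid use and pain contain arm, participant and time; for H3 the text is "Study arm will be considered a fixed effect, and participant and time will be considered random effects". None has a hospital term. Hospital is also missing from the covariate list in the key-outcomes section and from the baseline comparison list under preliminary analyses. Listed covariates enter only in additional analyses, as potential confounders if they differ by arm.

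**Cost and utility model (D.4, after Table E-7).** A mixed generalized linear model is fitted "as a function of patient assignment to microdosing (vs TAU), site fixed effects", together with patient characteristics "possibly not balanced at baseline, with random effects at patient and site levels". The word site is not defined there.

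**The concern.** The Aim 3b model contains a parameter that the data cannot inform. It serves health utility and every cost category, and so feeds QALYs and the ICER. To fit it, an analyst must drop a term or accept whatever the software returns for the site variance. That choice belongs in the plan, before the data are seen.

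The plan also treats site unevenly. PROPr utility is the quality-of-life outcome in H3, modelled without hospital, and the effectiveness measure in Aim 3b, modelled with site. No reason is given. Hospital could plausibly be prognostic for uptake: the primary outcome is read from hospital medication administration or prescription records, and adjunctive medication may be given "during induction based on hospital protocols". If uptake does differ by hospital, leaving the term out of H1 wastes some precision and leaves any chance imbalance between arms unadjusted.

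**Working it through.** **1. The plan's own figures.** D.2.12 gives 61% and 24% uptake, 80% power, 27 per arm. Two-sided alpha 0.05 is assumed, as none is stated. With mean proportion 0.425:

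n = [1.960 × √(2 × 0.425 × 0.575) + 0.842 × √(0.61 × 0.39 + 0.24 × 0.76)]² / 0.37² = (1.370 + 0.546)² / 0.1369 = 26.8, so 27. This reproduces.

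For pain, the minimum d is (1.960 + 0.842) × √(2/135) = 0.341, against the stated 0.34. This also reproduces. Neither figure involves hospital.

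**2. Site as fixed and random effect.** Let Z hold the site indicators, let the fixed-effect matrix X contain Z and arm, and let V = σ²I + τ²ZZ′. REML uses only contrasts K′y with K′X = 0. Because Z lies inside X, K′Z = 0 as well, so those contrasts do not depend on τ². Adding a patient random effect changes V but not this argument. Under ML the fitted residuals are unaffected by τ² while the log-determinant penalty grows with it, so the maximum is at τ² = 0.

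Numerical check: 270 simulated patients, three sites, normal outcome, σ² held at 1. X and Z together have 7 columns and rank 4.

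| Site variance | REML, site fixed + random | ML, site fixed + random | Arm estimate | REML, site random only |
|---|---|---|---|---|
| 0 | −129.368 | −120.53 | 0.285 | −150.80 |
| 0.01 | −129.368 | −121.49 | 0.285 | −139.31 |
| 0.1 | −129.368 | −123.98 | 0.285 | −130.22 |
| 1 | −129.368 | −127.29 | 0.285 | −130.20 |
| 10 | −129.368 | −130.73 | 0.285 | −132.25 |

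With both terms, REML is flat and ML falls steadily from zero. With the random effect alone the likelihood does have curvature, though three sites inform a variance poorly. The arm estimate is the same throughout.

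**3. Hospital left out of H1.** The documents give no hospital-level uptake or enrolment shares, so these are assumed: shares of 50/30/20%, 135 per arm, conditional odds ratio 2.0, and 4,000 simulated trials per scenario with simple 1:1 allocation. An odds ratio of 2.0 is about 61% against 44% uptake: (0.61/0.39)/(0.44/0.56) = 1.99, for which 135 per arm gives power 0.80.

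| Control uptake by hospital | Power, arm only | Power, arm + hospital | Type I error, without / with |
|---|---|---|---|
| 44/44/44% | 0.80 | 0.80 | 0.053 / 0.055 |
| 35/45/60% | 0.77 | 0.79 | 0.049 / 0.049 |
| 25/45/70% | 0.69 | 0.76 | 0.053 / 0.051 |

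**4. Chance imbalance.** In the same simulations the largest hospital's share differed between arms by more than 10 points in about 10% of trials. If instead each hospital enrolled 90 patients and the arms were fixed at 135 each, the number in one arm at a given hospital would have SD √(22.5 × 180/269) = 3.9, a 95% range of about 37 to 53.

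**The case against.** **Omitting hospital is a precision preference, not an error.** This largely stands. Patients are individually randomized, and simulated type I error stayed near 0.05. A reader might infer that the primary comparison is biased or invalid; it is not. At the plan's own effect of 61% against 24%, power with 135 per arm is essentially 1 whatever is done about hospital. The loss matters only if the effect is much smaller and hospitals differ markedly.

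**A gain in patient numbers cannot be read off a variance share.** A reader might multiply the share of outcome variance explained by hospital by 270. That arithmetic belongs to a linear model. In logistic regression a prognostic covariate does not shrink the standard error in that way; it changes the target to an odds ratio conditional on hospital.

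**Randomization is not at fault.** A reader might fault the plan for not stratifying by hospital. The three existing factors give 2 × 2 × 2 = 8 strata of about 34 patients (270/8). Adding hospital would give 24 strata of about 11 (270/24), with blocks of 4 to 8. Leaving hospital out is defensible.

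**Hospital effects may be small.** D.2.7 has trained study clinicians following an induction check-list, and nothing says that hospital protocols differ within this one system. This stands, and it is why no gain is one end of the range.

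**The cost model may do no harm.** A reader might infer that incremental cost is distorted through a rescaling of predicted means. That would need a log link, a non-zero site variance and predictions averaged over the site effect; the plan states none of these, and under ML the variance is zero. What remains is that the specification is redundant. It would be estimable if the two uses of site meant different units, such as hospital and clinic, or if the random term were an arm-by-site slope. The text says neither.

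**Conclusion.** Both points hold and both are minor. The Aim 3b model cannot be fitted meaningfully as written, because the site-intercept variance is not identified once every site has a fixed effect. This rests on reading site as the same unit in both places and the random effect as an intercept. Hospital is the natural reading, since Table E-7 costs the intervention from the index hospitalization. The numerical check is linear; no log-link model was tested, so no effect on incremental cost is claimed.

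The missing hospital term in H1 and H3 costs precision and protection against chance imbalance, nothing more. For H1 the power gain from including it is nil to 7 points over the assumed scenarios, and its true size cannot be found from the documents. The H3 models were not simulated.

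**What to change.** In Aim 3b, define site as the hospital of enrolment, keep the site fixed effects and the patient random effect, and delete the site-level random effect.

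In D.2.11, pre-specify hospital as a three-level fixed effect in the H1 logistic model, the H1 mixed models and the H3 models. Leave randomization unchanged.

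The cost is SAP wording and two degrees of freedom per model, using a variable known for every participant. The uptake odds ratio becomes conditional on hospital, so report the standardized risk difference beside it.
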